9.3.3 Severity of AEs

The Investigator will grade the severity of any AE using the definitions in the Table below. For each episode, the highest severity grade attained should be reported.

Severity of the Adverse Event

Mild	Grade 1 - Does not interfere with patient's usual function (awareness of symptoms or signs, but easily tolerated [acceptable]).
Moderate	Grade 2 - Interferes to some extent with patient's usual function (enough discomfort to interfere with usual activity [disturbing]).
Severe	Grade 3 - Interferes significantly with patient's usual function (incapacity to work or to do usual activities [unacceptable]).

9.4 SERIOUS ADVERSE EVENT REPORTING

9.4.1 Reporting Procedure for Investigators to PPD and Dompé Global Pharmacovigilance, Safety, and Surveillance

The Investigator must report all SAEs, regardless of presumed causal relationship, to PPD and Dompé Global Pharmacovigilance, Safety, and Surveillance (GPS2), by e-mail (preferred) or fax within 24 hours of learning of the event.

SAE reporting should be sent to:

- SAE Email address:
 - PPD
 - PPD
 - PPD

In case of failure of/lack of access to email, or fax, the event should be reported using the SAE hotline telephone number: PPD

If an SAE is reported via telephone, the telephone report should be followed by a written report using a reporting method described above (i.e., completion of paper form).

The Investigator should also report information on SAEs that continue after patient has completed his/her participation in the study (whether study completion or withdrawal) unless patient has withdrawn his/her consent.

Information on SAEs will be recorded on the SAE form approved by the Sponsor. In the SAE form, the Investigator shall clearly report any other concomitant medicinal product administered at the time of the SAE onset and shall assess the causal relationship (related or unrelated) of the SAE in respect to Oxervate treatment (that occurred during the previous DEFENDO Study) and any other concomitant medicinal product.

Additional follow-up information (e.g., test results, autopsy, and discharge summary) may be requested to supplement the SAE report form and can be attached as de-identified records. Follow-up reports (as many as required) should be completed and e-mailed/faxed following the same procedure and timeline above, marking the SAE form as “follow up Number XX”.

Whenever more than one SAE is observed, the Investigator should identify which is the primary SAE, i.e., the most relevant one. In any case, the Investigator is requested to record his/her opinion about the relatedness of the observed event(s) with the investigational medication.

In line with CT3 Detailed Guidance and International Conference on Harmonization (ICH) E2A provisions, although the Investigator does not usually need to actively monitor patients for AEs once the study has ended, if the Investigator becomes aware of a SAE occurring to a patient after that patient has ended his/her participation in the study – including the long-term follow-up (whether study completion or withdrawal), the SAE should be reported by the Investigator to the Dompé PPD Pharmacovigilance. Such “post-study cases” should be regarded for expedited reporting purposes as though they were study reports. Therefore, a causality assessment and determination of expectedness are needed for a decision on whether expedited reporting is required.

9.4.2 Conditions that should not be reported as SAEs

The conditions listed below, that may require hospitalization of a patient, are not considered to be SAE, and shall not be reported as such, but only need to be recorded in the CRF:

- Hospitalizations planned before entry into the DEFENDO Long-Term Follow-up Study, which is part of the normal treatment or monitoring of the studied indication and not associated with any deterioration in condition.
- Hospitalization for routine treatment or monitoring of the studied indication, not associated with any deterioration in condition.
- Hospitalization for treatments, which was elective or pre-planned, for a pre-existing condition that is unrelated to the indication under study and did not worsen.
- Hospitalization for general care not associated with any deterioration in condition.
- Treatment on an emergency, outpatient basis for an event not fulfilling any of the definitions of SAEs given above and not resulting in hospital admission.

In addition, the following situation shall not be considered SAE:

- Study endpoints
- Abnormal lab values or test results that do not induce clinical signs and/or symptoms and require intervention/therapy, i.e., are clinically significant.

9.4.3 Reporting Procedure to IRB/IEC and to Regulatory Authorities and Notification to NDA or BLA holder

SUSAR determined to be related to treatment with Oxervate shall be reported to the Regulatory Authority (FDA and non-US concerned Authority as applicable) by Dompé as soon as possible and in no event later than:

- (a) seven calendar days after becoming aware of the information if the event is fatal or life threatening; to be followed by any relevant information within eight days.
- (b) fifteen calendar days after becoming aware of the information if the event is neither fatal nor life threatening.

Dompé is also the BLA holder of Oxervate, therefore as Sponsor, Dompé must also submit safety information from the clinical study as prescribed by the relevant post-marketing safety reporting requirements (e.g., under Code of Federal Regulations (CFR) §§ 600.80). If the results of an investigation show that an ADR not initially determined to be reportable is reclassified as reportable, *Dompé* shall report such reaction in a written safety report as soon as possible, but in no event later than 7/15 calendar days after the determination is made.

In addition, each IRB/IEC/Regulatory Authority and Investigator will receive appropriate periodic safety updates as per applicable local requirements and regulations.

In addition to reporting the SAE to Dompé PPD, the Investigator must also comply with the requirements related to the reporting of SAEs to the local IRB which approved the study. The requirements of IRBs vary from one IRB to another; however, as a minimum requirement, the Investigators must promptly report all suspected unexpected serious adverse reactions (SUSAR) to their IRB.

In line with provisions set forth in 21CFR312, Dompé shall notify all participating Investigators in an Investigational New Drug (IND) safety report of any suspected adverse reaction that is both serious and unexpected and of potential serious risks, from clinical studies or any other source, as soon as possible, but in no case later than:

- seven calendar days after becoming aware of the information if the event is fatal or life threatening; to be followed by any relevant information within eight days.
- fifteen calendar days after becoming aware of the information if the event is serious but neither fatal nor life threatening.

The Investigators in turn shall notify their local IRB.

Copies of all correspondence relating to reporting of any SUSARs to the local IRB should be maintained in the Investigator's Files.

Dompé shall also notify the FDA in an IND safety report of potential serious risks, from clinical studies or any other source, as soon as possible after Dompé determines that the information qualifies for reporting, shall notify of:

- Any suspected adverse reaction that is both serious and unexpected. Dompé must report an AE as a suspected adverse reaction only if there is evidence to suggest a causal relationship between the drug and the AE.
- Findings from other studies that suggest a significant risk in humans exposed to the drug. Such a finding would result in a safety-related change in the overall conduct of the clinical investigation.
- Findings from animal or in vitro testing that suggest a significant risk in humans exposed to the drug.
- Increased rate of occurrence of serious suspected adverse reactions.

When SAEs are determined to be related to treatment with other medicinal products administered during the DEFENDO Long-Term Follow-up Study, the Sponsor will also forward the report to the NDA or BLA holder, manufacturer, packer, or distributor of the marketed drug.

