8.1.3 Safety Endpoints

- AEs assessed throughout the study.
- Slit-Lamp Examination results.
- External Ocular Examination results.

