9 EVALUATION OF ADVERSE EVENTS AND SAFETY INFORMATION

9.1 DEFINITIONS

Adverse Event

An **Adverse Event (AE)** is defined as any untoward medical occurrence in a patient or clinical investigation patient administered a pharmaceutical product and which does not necessarily have a causal relationship with this treatment. An AE can therefore be any unfavorable and unintended sign (including an abnormal laboratory finding), symptom, or disease temporally associated with the use of a pharmaceutical product, whether considered related to treatment. This definition includes an exacerbation of preexisting medical conditions or events, historical conditions do not present prior to study treatment in the DEFENDO Study, which reappear following study treatment, intercurrent illnesses, hypersensitivity reactions, drug-drug or drug-food interactions, medication errors, overdose (both intentional or unintentional), drug misuse/abuse, false positive laboratory test, or the significant worsening of the disease under investigation.

Adverse Drug Reaction

An **Adverse Drug Reaction (ADR)** is defined as an adverse experience, which is reasonably likely to have been caused by the drug. An adverse reaction, in contrast to an AE, is characterized by the fact that a causal relationship between a pharmaceutical product and an occurrence is suspected. Medical judgment should be used to determine the relationship, considering all relevant factors, as applicable, including pattern of reaction, temporal relationship, de-challenge or re-challenge, confounding factors such as concomitant medication, concomitant diseases, and relevant history. Adverse drug reactions may arise from use of the study treatment in the DEFENDO Study within or outside the terms of the marketing authorization or from occupational exposure. Conditions of use outside the marketing authorization include off-label use, overdose, misuse, abuse, and medication errors, occupational exposure.

The Investigator should carefully evaluate the relationship between the event and previous treatment with OXERVATE or any medicinal product administered at the AE onset. The Investigator should use the following information to help make their decision.

Arguments that may suggest a reasonable causal relationship could be:

- The event is consistent with the known pharmacology of the drug.
- The event is known to be caused by or attributed to the drug.

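### Protocol 9.4.2 exempts study endpoints from SAE status without qualification, although the endpoints include corneal healing, visual acuity, eye-examination findings and AEs themselves

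*Protocol*

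**What the plan says.** Protocol 9.4.2 contains two lists. The first describes hospitalisations and emergency outpatient care that go into the CRF but are not reported as SAEs. The second opens with "In addition, the following situation shall not be considered SAE" and has two entries. One is "Study endpoints", with no definition, severity limit or alternative reporting route. The other reads "Abnormal lab values or test results that do not induce clinical signs and/or symptoms and require intervention/therapy, i.e., are clinically significant".

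Section 8.1 lists the endpoints: corneal epithelial healing, corneal sensitivity, Schirmer I, TFBUT, BCDVA and quality of life. Section 8.1.3 adds three safety endpoints: "AEs assessed throughout the study", "Slit-Lamp Examination results" and "External Ocular Examination results".

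On reporting, 9.4.1 says "The Investigator must report all SAEs, regardless of presumed causal relationship", with a 24-hour limit. Section 9.1 sets the seriousness criteria, which include inpatient hospitalisation, lasting or significant disability and important medical events, and it makes death an SAE in every case. Section 9.3 says that untoward occurrences in the long-term follow-up are to be treated, recorded and reported as AEs and/or SAEs.

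SAP 6.1 and SAP Appendix 2 (item 14.3.2) provide a listing of SAEs during the extended follow-up.

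**The concern.** Section 9.4.2 is where a site would look when deciding whether an event has to go out as an SAE. Its unqualified entry covers a category that, in this trial, overlaps with the harms of greatest interest. Protocol section 3 names persistent epithelial defect, ulceration, melting, perforation and infectious keratitis as complications of the disease. Such events would generally show up as a cornea that is not healed, as slit-lamp findings or as lost acuity, and all of these are endpoints.

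Long-term safety is a primary objective (4.1). If an event of this kind were treated as exempt, four things would be affected: its SAE status, the 24-hour report, the SUSAR assessment (which under 9.1 requires the event to be serious) and its entry in the SAE listing. Section 6.2 allows commercial OXERVATE during follow-up, and 9.3.2 requires causality to be assessed against it, so an exempted event could also be a suspected drug reaction. The four sites could resolve the conflict differently.

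**Working it through.** No arithmetic applies, because the point concerns a reporting rule. The check sets the texts side by side.

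1. **Scope of the exemption.** The entry in 9.4.2 is not limited to efficacy endpoints, to measurements or to non-serious outcomes. No visible section says which endpoints it means. Part of section 8 is redacted, but every endpoint relied on here can be read.

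2. **What falls inside it.** Section 8.1 brings in corneal healing and BCDVA. Section 8.1.3 brings in slit-lamp results, external ocular results and AEs. Because AEs are on the list, a literal reading would exempt every AE.

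3. **Against the seriousness criteria (9.1).** An event is serious if it meets any one criterion, and 9.1 contains no exception for endpoints. A corneal perforation, for example, could plausibly qualify as an important medical event needing intervention to prevent disability. Section 9.1 would then make it an SAE, and 9.4.2, read literally, would say it is not one. The same clash arises for death, which 9.1 always counts as an SAE.

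4. **Against 9.3.** This section addresses the long-term follow-up directly and sends untoward events to AE and/or SAE reporting. It also says that a non-serious AE that becomes serious follows the SAE procedure. It has no exception for endpoints either.

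5. **Against 9.4.1.** All SAEs are to be reported within 24 hours. This duty depends on what counts as an SAE, so it does not settle the conflict by itself. It does show what is lost if 9.4.2 is applied first.

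6. **Against the other exclusions in 9.4.2.** Each of the four hospitalisation exclusions applies only where there is no deterioration or worsening. The emergency outpatient exclusion applies only where no SAE definition is met. The endpoint entry alone has no such limit.

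7. **What is not lost.** The AE definition in 9.1 includes "or the significant worsening of the disease under investigation", and 9.2 makes clinically relevant untoward changes in protocol parameters AEs. Those two texts decide AE status, not SAE status, so they do not themselves contradict 9.4.2. They do mean that the event is still recorded. SAP 6.1 then tabulates AEs by maximum severity and lists all events in the database.

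8. **The second entry.** In the abnormal-results entry, the closing phrase can attach to the exempted results or to the condition they fail to meet. The second is the ordinary sense and the likely intent, but the sentence does not secure it.

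No section ranks 9.4.2 below 9.1, 9.3 or 9.4.1, or the reverse.

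**The case against.** The strongest reply is that the entry has a sensible narrow meaning. The endpoints in 8.1 are percentages and changes in measurements, not clinical events. Ulceration and perforation appear in the disease background and not in the endpoint list. On this view 9.4.2 says only that a result such as an unhealed cornea is not by itself an SAE. The limits on the other exclusions also suggest that nobody meant to exempt serious worsening. This is plausible and may well be what was intended. But 9.4.2 does not say it, and AEs, which 8.1.3 names as an endpoint, are events.

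A second reply is that the events remain visible as AEs. That stands, and it confines the problem to the SAE flag and the reporting that depends on it.

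Several stronger readings are tempting, and the documents do not support them:

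- **The protocol tells sites to withhold serious events.** Sections 9.1, 9.3 and 9.4.1 point toward reporting. The text is contradictory, not an instruction to withhold.
- **No event in this study could ever be an SAE.** This follows literally from listing AEs as an endpoint, but it would empty all of 9.4. It shows loose drafting and does not show how sites would act.
- **Clinically significant test results are exempt.** The second entry is poorly worded, but its ordinary sense can be recovered.

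**Conclusion.** The concern holds as a rule that is wrong as written and should be fixed. The endpoint exemption in 9.4.2 is unqualified and, applied literally, conflicts with the seriousness criteria in 9.1, with 9.3 and with 9.4.1.

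The consequence is limited to SAE classification, the 24-hour report, the SUSAR assessment and the SAE listing; AE recording and AE tables are unaffected. The documents give no basis for estimating how often a site would misclassify an event, so no numerical size is attached. A reader might infer that serious events have in fact gone unreported, but nothing in the protocol or SAP shows that.

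The conclusion assumes that no unseen document, such as a safety plan or site training material, already restricts the entry to measurements. If one does, the protocol wording still needs to match it.

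**What to change.** Reconcile 9.4.2 with 8.1, 8.1.3, 9.1, 9.3 and 9.4.1 in one of two ways:

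- delete the endpoint entry; or
- replace it with a sentence such as: An efficacy assessment result is not by itself an SAE, unless the associated event meets a seriousness criterion in section 9.1.

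Reword the abnormal-results entry so that it clearly exempts only results that are not clinically significant.

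If follow-up is already complete, check the recorded AEs against the 9.1 criteria before the SAE listing is finalised, and process any reclassified event under 9.4.

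The cost is a short amendment, which under 13.4 generally needs IRB approval and a signed investigator page before use, or a clarification to the four US sites. It may also produce a few more SAE reports.

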3 BACKGROUND INFORMATION

The DEFENDO Study was aimed at evaluating the efficacy and safety of OXERVATE™ 0.002% (20 mcg/mL) cenegermin-bkbbj ophthalmic solution administered 6 times daily for 8 weeks in patients with Stage 1 neurotrophic keratitis (NK).

The current study is a long-term study evaluating the clinical outcomes of patients at 24 months and 30 months after completion of the DEFENDO Study.

NK, also known as neurotrophic keratopathy/keratitis, is a rare degenerative corneal disease caused by an impairment of corneal nerve innervation leading to a decrease or absence in corneal sensation. The cornea is an avascular tissue that is provided with the richest innervation of all body tissues via the trigeminal nerve. Corneal hypoesthesia or anesthesia and decreased reflex tearing resulting from impaired corneal innervation can lead to a corneal epitheliopathy with a subsequent breakdown of the corneal epithelium, leading to potential visual impairment. Abnormal corneal sensation and epithelial defects with a poor tendency for spontaneous healing are the primary clinical manifestations of NK, which increase the risk for corneal complications associated with vision loss such as a persistent epithelial defect (PED), ulceration, melting, perforation, and infectious keratitis. NK has been divided into three stages according to the Mackie classification scheme ([Appendix 4](#)) and treatment recommendations are based on the severity of corneal involvement. ^[1]

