NOTE: In general, hospitalization means that the individual remained at the hospital or emergency ward for observation and/or treatment (usually involving an overnight stay) that would not have been appropriate in the physician's office or an out-patient setting. Complications that occur during hospitalization are AEs. If a complication prolongs hospitalization or fulfills any other serious criteria, the event is serious. When in doubt as to whether "hospitalization" occurred, the event should be considered serious.

- Results in persistent or significant disability/incapacity.

NOTE: This definition is not intended to include experiences of relatively minor medical significance such as uncomplicated headache, nausea, vomiting, diarrhea, influenza, or accidental trauma (e.g., sprained ankle), which may interfere or prevent everyday life functions, but do not constitute a substantial disruption.

- Is a congenital anomaly/birth defect.
- Is medically significant or important medical condition, i.e., an important medical event that based upon appropriate medical judgment, may jeopardize the patient, and may require medical or surgical intervention to prevent one of the outcomes listed above.

An important medical condition is an event that may not result in death, be life-threatening, or require hospitalization but may be considered a SAE when, based upon appropriate medical judgment, it may jeopardize the patient and may require medical or surgical intervention to prevent one of the outcomes listed above. Examples of such medical events include allergic bronchospasm requiring intensive treatment in an emergency room or at home, blood dyscrasias or convulsions that do not result in patient hospitalization, or the development of drug dependency or drug abuse.

Pre-planned hospitalization or hospitalization for routine treatment or monitoring of the studied indication, not associated with any deterioration in condition are not considered to be SAEs. These events must be recorded in the AE page of the CRF where a variable will be ticked to indicate that they are not SAEs.

Death shall always be reported as SAE. Cause of death shall always be specified when known.

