9.2 MONITORING FOR ADVERSE EVENTS

At each Follow Up visit, after the patient has had the opportunity to spontaneously mention any problems, the Investigator or appropriate designee should inquire about AEs by asking the standard questions:

- “Have you had any health problems since your last study visit?”
- “Have there been any changes in the medicines you take since your last study visit?”

AEs should be reported for any clinically relevant change in concomitant condition(s) that is the result of an untoward (unfavorable and unintended) change in a patient’s medical health. Anticipated day-to-day fluctuations of preexisting conditions that do not represent a clinically significant exacerbation or worsening need not be reported as AEs. Changes in any protocol-specific [ocular or] systemic parameter evaluated during the study are to be reviewed by the Investigator. In addition, the patient’s responses to any questionnaire utilized during the study are to be reviewed by the Investigator. Any untoward (unfavorable and unintended) change in a protocol-specific parameter or questionnaire response that is clinically relevant is to be reported as an AE. These clinically relevant changes will be reported regardless of causality.

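### The test-result exemption in Protocol 9.4.2 is garbled and, as written, can conflict with the medically-important SAE criterion in 9.1

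*Protocol*

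**What the plan says.** Protocol 9.4.2 has two lists. The first covers hospital and outpatient care. One of its bullets is expressly subordinate to the definitions: "Treatment on an emergency, outpatient basis for an event not fulfilling any of the definitions of SAEs given above" and not leading to admission. The second list opens with "In addition, the following situation shall not be considered SAE" and has two bullets. One says only that study endpoints are exempt. The other reads "Abnormal lab values or test results that do not induce clinical signs and/or symptoms and require intervention/therapy, i.e., are clinically significant". Neither bullet in the second list refers back to the SAE definitions.

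Protocol 9.1 counts as an adverse event "any unfavorable and unintended sign (including an abnormal laboratory finding), symptom, or disease temporally associated with the use of a pharmaceutical product", so a finding can be an AE without being felt. Among the seriousness criteria is an event that "Is medically significant or important medical condition", explained as one that on medical judgment "may jeopardize the patient, and may require medical or surgical intervention to prevent one of the outcomes listed above".

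Protocol 9.2 adds: "Any untoward (unfavorable and unintended) change in a protocol-specific parameter or questionnaire response that is clinically relevant is to be reported as an AE".

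Protocol 9.4.1 requires the investigator to report every SAE within 24 hours of learning of it. SAP 6.1 and SAP Appendix 2 (item 14.3.2) plan a listing of SAEs.

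**The concern.** An exemption for test results normally serves to keep trivial abnormalities out of expedited reporting. This one closes by describing the exempt results as clinically significant and as needing therapy, which is the opposite of trivial. An investigator who follows the printed sentence could decline to classify as serious a result that 9.1 would make serious.

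SAE status controls three things here: the 24-hour report to the sponsor (Protocol 9.4.1), eligibility for the expedited regulatory and investigator reports that require seriousness (Protocol 9.4.3), and entry in the SAE listing. Long-term safety is one of the two primary objectives (Protocol 4.1), so the rule deciding which events count as serious should have one meaning.

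**Working it through.** No arithmetic applies. The documents give no figure on this point, so the check is a comparison of wording.

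Let S mean that the result induces clinical signs and/or symptoms, and T that it requires intervention or therapy. The bullet can be read in three ways:

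- **Reading A:** the word *not* governs only *induce*. Exempt set = (not S) and T.
- **Reading B:** the word *not* governs the whole conjunction. Exempt set = not (S and T) = (not S) or (not T).
- **Reading C:** the probable intent, neither S nor T, and so not clinically significant. Exempt set = (not S) and (not T). This needs words that the sentence does not contain.

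| Result | A | B | C |
|---|---|---|---|
| S and T | not exempt | not exempt | not exempt |
| S, not T | not exempt | exempt | not exempt |
| not S, but T | **exempt** | **exempt** | not exempt |
| neither S nor T | not exempt | exempt | exempt |

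The third row decides the matter. Both readings of the text as printed exempt a result with no sign or symptom that needs intervention. Only the reading that repairs the sentence does not. Reading A also leaves harmless results (the last row) outside the exemption, which suggests that it was not intended.

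Next, compare the third row with 9.1. The medically-important criterion has two parts: possible jeopardy to the patient, and possible need for intervention to prevent one of the listed outcomes. Signs and symptoms are not mentioned. Call this criterion J.

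- Results with (not S), T and J: 9.1 says SAE and 9.4.2 says not an SAE. This is a contradiction.
- Results with (not S) and T that meet neither J nor any other seriousness criterion: both sections say not an SAE. There is no conflict.

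The conflict is therefore conditional. Needing therapy does not by itself make a result serious under 9.1.

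Finally, is there a rule of precedence? The outpatient-emergency bullet carries one, because it applies only where no SAE definition is met. The test-result bullet carries none, its lead-in is categorical, and neither section says which prevails. Nothing in the text resolves the contradiction.

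**The case against.** The best defence is that this is a slip in the scope of a negation. The closing gloss on clinical significance shows what was meant, and a sensible investigator would apply Reading C. That is probably right about intent. It does not rescue the sentence, because Reading C has to be supplied by the reader and this is an operative reporting rule.

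Four stronger claims are tempting, and the documents do not support them.

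- **That the rule is unsafe because the disease silences symptoms.** Protocol section 3 does describe the disease as "leading to a decrease or absence in corneal sensation". But the bullet requires the absence of signs as well as symptoms, at least on a plain reading of *and/or*. Reduced sensation can suppress symptoms, not signs. The cornea is examined by slit lamp at both visits, and a defect seen there is ordinarily a sign, so it falls outside the bullet. Stage 1 is reduced rather than absent sensation, and the patient leaflet in Protocol Appendix 3 names eye pain as a common side effect. The sensation argument is at most supporting.
- **That every result needing treatment is wrongly exempted.** The full 9.1 criterion must also be met.
- **That the primary safety result is biased downward.** Under 9.2 clinically relevant changes are still AEs. They stay in the AE tables by organ class, severity and relationship (SAP 6.1) and in AE listing 16.2.7.
- **That the effect can be shown as a shift in an SAE rate and its confidence limit.** For SAEs the SAP names a listing and no rate or interval. The 37 patients are a ceiling, and no count of affected results is given.

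One further objection stands in part. Visual acuity and centrally read healing are study endpoints (Protocol 4.3 and 8.1), so the neighbouring study-endpoints bullet may already exempt them. Protocol 8.1.3 also lists AEs and slit-lamp results as safety endpoints. Correcting the negation alone might then change nothing for those findings, which is why the fix needs a second sentence covering both bullets.

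**Conclusion.** The point holds as an internal inconsistency in a safety-reporting rule. Both grammatical readings of the 9.4.2 bullet withhold SAE status from results that induce no sign or symptom but need intervention. Where such a result meets the medically-important criterion, 9.1 and 9.4.2 give opposite answers and the protocol does not say which governs.

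The possible consequence is that SAE classification, the 24-hour report and entry in the SAE listing are omitted or delayed. AE recording is not affected. The number of events is unknown and cannot be estimated from the documents; it may be zero. The conclusion assumes that investigators apply the sentence as printed. If all of them read it as probably intended, this bullet creates no conflict with 9.1.

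**What to change.** Reconcile 9.4.2 with 9.1 in one amendment:

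1. Correct the negation, for example: *Abnormal laboratory values or test results that neither induce clinical signs or symptoms nor require intervention, i.e. are not clinically significant.*
2. Add a sentence making the whole second list, including the study-endpoints bullet, subordinate to the definitions: *These exemptions apply only to events that meet no seriousness criterion in 9.1.*

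If visits are already complete, compare the recorded AEs with the 9.1 criteria before the SAE listing is finalised, and say in the study report that this was done.

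The cost is one or two sentences of protocol text and possibly a few more SAE forms. No analysis, endpoint or visit changes.
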